### **4.3 Secondary goal**

Determination of the improvement of the balance by means of the berg balance scale.

### **4.4 Safety goals**

A safety goal is the fall prophylaxis. The safety is to be ensured by the bar, on which the patients can hold on, if they lose the balance. In addition, the patients should as far as possible achieve a walking speed with which they can safely cross a street.

## **5 TARGETS OF THE STUDY**

### **5.1 Primary target**

Improving walking speed by 18 cm/sec would be a successful outcome (Fulk et al, 2011). Whether there is a difference between individual balance training and group balance training is to be determined. To be able to cross a pedestrian traffic light, a walking speed of 1.0-1.2 m/sec would be necessary (Hüter-Becker, et al., 2005). This would be the ideal value.

### **5.2 Secondary target**

If not already achieved in the initial assessment, a score of 45/56 points should be achieved for reassessment in the berg balance scale (BBS). That's the cut-off value (Schädler, et al., 2012).

### **5.3 Safety targets**

The risk of falling should be reduced. In order to be able to prove this, patients should achieve a score of at least 45 in the reassessment of the BBS. In addition, a walking speed of 0.8 m/sec in a 10m walk test should be achieved.

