### Falling risk

The Berg Balance Scale is used to determine the risk of falling. The BBS detects deficits at both activity and body function levels. It consists of 14 items. Scaling takes place from 0 points (not possible) to 4 points (independently possible). This results in a total score of 56 points. The individual items are shown in the template in the appendix.

Very good intertester reliability was found in a study of 112 stroke patients (Mao, Hsueh, Tang, Sheu, & Hsieh, 2002).

The best values in terms of validity resulted from the combination of the BBS with the walking speed. This gave a specificity of 70% and 91% sensitivity (Schädler, et al., 2012).

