## **8.2.3 Recording safety targets**

### **8.2.3.1 Serious Adverse Event (SAE)**

A SAE would be a fall of the patient. If this has happened, a fall protocol will be created on the RehaClinic intranet. It records how the fall came about and under what circumstances, when the fall took place, and which people were present. The patient is examined by the ward physician and, where appropriate, measures for further examination or treatment are initiated. If the patient later describes the fall, as unobserved, the same procedure nevertheless takes place.

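### Section 5.3 sets out to prove a reduction in fall risk from end-of-treatment levels alone, so a patient already above both levels who is unchanged or worse can meet the target

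*Combined protocol and SAP*

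**What the plan says.** Section 5.3 (Safety targets) opens with an objective about change: "The risk of falling should be reduced". To prove it, "patients should achieve a score of at least 45 in the reassessment of the BBS". A second criterion follows: "In addition, a walking speed of 0.8 m/sec in a 10m walk test should be achieved". The section mentions no baseline value or change score, and no restriction to patients who start below either level.

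Section 5.2 (Secondary target) uses the same scale, cut-off and time point, but with a condition: "If not already achieved in the initial assessment, a score of 45/56 points should be achieved for reassessment". The secondary goal in 4.3 is also worded as a change: "Determination of the improvement of the balance by means of the berg balance scale".

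Other relevant places:

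- Section 5.1 names an improvement of 18 cm/sec as a successful outcome for walking speed, so the plan already uses one target based on change.
- Sections 8.1, 8.2.1 and 8.2.2 schedule the walk test and the BBS before the first session and after the last one.
- Section 7.1 requires walking ability with aids and sets no upper BBS or speed limit at entry.
- Section 10 plans means, standard deviations and frequencies for the assessments. It announces an odds ratio between the groups without defining the binary outcome.
- Section 10.3.3, headed Safety analysis, deals only with training the physiotherapists.
- Section 8.2.3.1 records falls: "A SAE would be a fall of the patient". Section 5.3 does not use them.

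**The concern.** A reduction compares two time points, and a final level describes only one. Meeting the levels in 5.3 therefore mixes patients who improved with patients who never needed to, and with some who got worse but had room to spare. The rule also errs the other way, because a large gain that ends just short of 45 earns nothing.

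Section 5.2 shows that the authors expected some patients to start at 45 or more. Without the same condition in 5.3, the number reaching the target partly reflects who was recruited. A report that followed 5.3 literally could state that fall risk was shown to be reduced when the data show only that some patients finished, and perhaps started, above the levels.

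**Working it through.** The plan gives no figure for this target, so there is none to reproduce. The check applies the rule as written and then sizes its BBS part.

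**1. The rule applied to single patients.** Inputs: BBS range 0 to 56 (section 8.2, Falling risk: "This results in a total score of 56 points"); BBS part met if the reassessment score is at least 45 (5.3).

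| Baseline BBS | Reassessment BBS | Change | BBS part of 5.3 |
|---|---|---|---|
| 50 | 50 | 0 | met |
| 45 | 45 | 0 | met |
| 54 | 46 | −8 | met |
| 44 | 45 | +1 | met |
| 20 | 44 | +24 | not met |

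Reading the words introducing the speed criterion as requiring both parts, the first four patients meet the full target only if their final walking speed is also at least 0.8 m/sec. That criterion is itself a final level: a patient who is slower than at baseline but still at 0.8 m/sec or more meets it. The fifth patient fails whatever the speed.

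**2. The 5.2 condition applied to the same patients.** Limiting the count to those below 45 at baseline leaves the fourth and fifth rows. The first three, who did not improve, drop out of the count.

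**3. Size of the BBS part if nothing changes.** If each reassessment score equals its baseline score, the share meeting the BBS part is P(baseline BBS ≥ 45). The documents give no baseline distribution, so I assume a normal one with mean 35 to 45 and SD 8 to 12. With a continuity correction, the share is 1 − Φ((44.5 − mean)/SD).

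| Mean | SD | (44.5 − mean)/SD | Share at 45 or more |
|---|---|---|---|
| 35 | 8 | 1.188 | 0.12 |
| 35 | 12 | 0.792 | 0.21 |
| 40 | 8 | 0.563 | 0.29 |
| 40 | 12 | 0.375 | 0.35 |
| 45 | 8 | −0.063 | 0.52 |
| 45 | 12 | −0.042 | 0.52 |

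The range is about 12% to 52%, or 1 to 5 patients in an arm of 10 (10 × 0.12 = 1.2; 10 × 0.52 = 5.2).

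**4. From the BBS part to the full target.** With no change, the full target is met by patients already at or above both levels. They are a subset of those at 45 or more, so the figures in step 3 are upper bounds.

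**5. Effect of the baseline condition.** A simulation added assumed measurement error (SD 2 at each test), kept scores within 0 to 56, and let the baseline mean run from 35 to 50 with SD 8 or 12. With zero true change, 12% to 75% of all patients met the BBS part, and 22% to 32% of those had scored lower than at baseline. Among patients below 45 at baseline, only 3% to 17% reached 45. All inputs to this step are assumptions.

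**The case against.** The strongest reply is that 5.3 is a rehabilitation goal in a small descriptive pilot. It says what patients should achieve. It defines no responder analysis and compares no arms. Section 10.2 says the 20 patients serve descriptive statistics and a later sample size calculation, and 10.1 concedes that little can be concluded. The condition in 5.2 stands directly above and might be taken as understood. This stands as a limit on the consequence: no error rate or sample size depends on 5.3. It does not repair the wording, because 5.3 claims proof of a reduction and neither repeats nor refers to the condition in 5.2.

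A reader might infer more than the documents support:

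- **That a final BBS of 45 is sufficient.** On that reading a fall from 54 to 46 would by itself count as reduced risk. Section 5.3 also asks for 0.8 m/sec, so such a patient meets the full target only if fast enough as well.
- **That the plan's own accuracy figures show the cut-off failing.** Section 8.2 says of BBS combined with walking speed: "This gave a specificity of 70% and 91% sensitivity". It gives no cut-offs and does not define the outcome being classified, so error rates for the 5.3 rule cannot be derived from it.
- **That 5.2 and 5.3 classify the same patient differently.** Section 5.2 does not say how a patient already at 45 is counted, and neither section defines a formal classification. What can be said is that 5.3 omits a condition that 5.2 states.
- **That chance imbalance in baseline BBS carries straight into a comparison of arms.** No such comparison is tied to 5.3, and the odds ratio in section 10 has no stated outcome.
- **That falls are ignored.** They are documented under 8.2.3.1, and 9.2 and 9.3 provide for SAEs to be entered in the CRF and listed in the annual safety report. They are only absent from the proof offered in 5.3.

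The objection that the size rests on assumed inputs is also fair. At mean 45 and SD 12, the normal model puts about 17% of patients above the scale maximum (1 − Φ((56.5 − 45)/12) = 1 − Φ(0.958) = 0.17). The percentages are therefore illustrative.

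**Conclusion.** The point holds for section 5.3 as written. Neither the BBS level nor the speed level, alone or together, can show a reduction in fall risk. That conclusion follows from the wording and needs no assumption.

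The size does need assumptions. If no patient changed, about 12% to 52% would meet the BBS part, given a baseline mean of 35 to 45 and SD of 8 to 12. The share meeting the full target can be no larger, and the documents give nothing from which to say how much smaller it is.

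The consequence is a potentially misleading safety statement in a descriptive pilot. It would go too far to say that the trial will reach a wrong safety conclusion, since no analysis of this target is specified. The correction is still worth making, because it changes what the trial can say about fall risk and needs only data already planned.

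**What to change.** Reconcile 5.3 with 5.2, and add the matching analysis to section 10.3.3:

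- Describe fall risk by change from baseline in BBS and in walking speed, by arm. If the arms are compared, adjust for the baseline value.
- Report attainment of each threshold only among patients below that threshold at baseline, with the denominator shown.
- List patients who start at or above a threshold and finish below it.
- Report recorded falls by arm alongside these results.
- Replace *prove* with *describe*.

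The cost is a few sentences and a little descriptive work on BBS, walking speed and fall records that are already collected. The downside is a smaller denominator for the threshold counts, which matters with 10 patients per arm. Under the assumptions in the working, about 1 to 5 of 10 patients would leave the BBS count.

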## **6 DESIGN AND EXPIRATION OF THE STUDY**

### **6.1 General design and justification of the design**

A controlled, randomized, open pilot study with parallel group design will be conducted.

In each case, ten patients are recruited randomly into the intervention group or control group. It does not pay attention to gender distribution. Each patient takes about three to four weeks to participate in the study. There are three weeks of intervention time.

The screening begins with the registration of the patient, because then usually already a preliminary discharge report, or referral report exists. On the day of arrival the medical admission takes place and the screening is checked. On the second day the Investigator visit the patient and explain to him about the possible participation in the study. He receives the consent form with the explanations from me and is informed that he will answer further questions, e.g. for medical safety to the attending physician could turn. With the signed consent, the randomization and accordingly the planning of the therapies, including initial and reassessment. Depending on the day of arrival, the intervention may begin in the first or second week. With the allocation, the therapists will also be informed, since they are not allowed to do any additional balance training in the therapy. When the sixth balance training is done, the reassessment takes place the next day.

This is an ongoing process for each patient.

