Goal:	
Goal: A suitable sample size is to be determined for a larger follow-up study and the study design should be checked for feasibility.
 
Question: In stroke patients, is there a difference between individual and group balance training in terms of improving walking speed?
 
Hypothesis: individual balance training has a better impact on walking speed than group balance training.
 
Primary outcome: gait speed → 10m walking tests
 
Secondary outcome: Berg-Balance Scale, FAC

Participants:	It will recruit 20 patients after stroke at the RehaClinic Kilchberg.
Study design:	controled, randomized, open pilot study with paralell groups - monocentric
In/Exclusion criteria:	Inclusion: min. 18 years, stroke starting from rehabilitation phase B, ability to understand therapy instructions, walkable with aids Exclusion: Neurodegenerative disease, non-stroke dizziness, cardiopulmonary insufficiency, polyneuropathy, peripheral vascular disease
Experimental intervention:	individual balance training: after the initial assessments, the three week intervention time begins, which is completed with the reassessments.  The patients receive 2x weekly individual balance training for 25 minutes each.  This runs in addition to the normal, prescribed rehabilitation program. The rehabilitation program includes at least 3 therapies daily. These may be group therapies, speech therapy, occupational therapy, neuropsychology and physiotherapy adapted to the needs of the patient. In physiotherapy and occupational therapy no balance training may be performed during the intervention period.
Controle intervention:	The patients receive 2x weekly group balance training for 25 minutes each.  This runs in addition to the normal, prescribed rehabilitation program. The rehabilitation program includes at least 3 therapies daily. These may be group therapies, speech therapy, occupational therapy, neuropsychology and physiotherapy adapted to the needs of the patient. In physiotherapy and occupational therapy no balance training may be performed during the intervention period.  In group therapy are 3 to 6 patients with different neurological diagnoses. As it is usual in rehabilitation everyday life.
Number of participants:	In total, 20 patients should be recruited. 10 in the intervention group and the other half in the control group.

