## **6.4 Randomization**

The randomization was prepared and the sealed envelopes numbered in order. Randomization was done using a list randomizer (<https://www.random.org/lists/>). The list is not publicly available.

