## **6.5 Mask, Blinding**

There is no blinding. Compliance with the blinding is hardly feasible in this setting. The patients recognize which group they are in and the group room is freely accessible and accessible by my colleagues.

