# **7 PARTICIPANTS**

Adult patients with strokes from rehabilitation phase B are recruited as long as they are able to walk with aids. It is a monocentric study in the RehaClinic Kilchberg. There, a total of 20 patients will be recruited over a 3-month period. Since it is a pilot study, I would look for a solution in the discussion, if the number of participants would not be reached. The patients who are already inpatients are recruited insofar as the discharge date is far enough in the future and the patients who have recently arrived there.

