## **7.3 Assignment to study groups**

The randomization was prepared and the sealed, opaque envelopes numbered in order. The randomization list is not public. Only I have access to it. The procedure is based on the order of consent, so that the allocation can not be manipulated.

After signing the consent form, I go with this to one of my direct supervisor ([name]) show her the consent and give them access to the envelopes (in a lockable closet). You open the envelope and show me which group has been assigned. I label the envelope and lock it again and lock it into my spint.

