### **10.2 Sample size calculation**

It is planned to recruit 20 patients to RehaClinic Kilchberg. This results in 10 patients each for the experimental group and the control group. This number is based more on the temporal than on the statistical factor. It serves only for the descriptive statistics in order to be able to make already first assumptions and to be able to carry out a SampleSize calculation. If this number is not reached by the end of April, the pilot study will nevertheless end. This should ensure the writing of the master thesis, so that it can be delivered on time.

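### Allocation is not protected from anticipation: the enrolling investigator holds the list and sees every assignment, and a fixed ten-per-arm list could still be partly counted down after custody is moved

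*Combined protocol and SAP*

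**What the plan says.** The arm totals are fixed in three places: Section 6.1 ("In each case, ten patients are recruited randomly into the intervention group or control group"), the synopsis ("In total, 20 patients should be recruited. 10 in the intervention group and the other half in the control group") and Section 10.2 ("This results in 10 patients each for the experimental group and the control group"). On sequence generation, Section 6.4 says "Randomization was done using a list randomizer". It describes no blocks or strata, and does not state which entries were put in or how many.

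Section 6.5 states "There is no blinding". The investigator pre-screens referral reports (synopsis, time plan), approaches and consents patients (6.1, 7.2) and normally delivers the training (3.2). Under Section 7.3 the investigator is the only person with access to the list. After consent a supervisor opens the next numbered, opaque envelope: "You open the envelope and show me which group has been assigned". The investigator then labels the opened envelope and keeps it locked away. The stated safeguard is "The procedure is based on the order of consent, so that the allocation can not be manipulated".

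Three other provisions matter. Section 7 admits current inpatients: "The patients who are already inpatients are recruited insofar as the discharge date is far enough in the future". Section 7.4 gives a drop-out's place to the next patient who consents. Section 10.2 ends the study at the end of April even if 20 patients have not been reached.

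**The concern.** Opaque envelopes opened by a supervisor after signed consent stop an envelope being chosen or exchanged. They do not stop an allocation being foreseen, and taking patients in order of consent does not help if the person who decides when to seek consent knows or can guess what comes next.

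There are two routes to that knowledge. The direct one is the list itself, which the enrolling investigator holds. The second survives a change of custody: with known totals of ten and ten, and every past allocation seen, the places left in each arm can be counted. The arm that is behind is the better guess, and once one arm is full the rest is certain.

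The plan leaves some room for this knowledge to act. The approach to current inpatients can be timed, and Sections 7 and 7.1.2 contain judgement items (enough stay remaining, suspected non-compliance). The stated hypothesis favours individual training. At stake is the between-arm difference in walking speed, and through it the effect size that Sections 4.1 and 10 carry into the sample size calculation for a follow-up RCT.

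**Working it through.** **The plan's own figure.** 20 / 2 = 10 per arm, which agrees. Section 10.2 bases the number on the timetable, so there is no power calculation to reproduce.

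**Assumption.** One shuffled list of 10 individual-balance (IB) and 10 group-balance (GB) labels, m = 10, with C(20,10) = 184,756 equally likely orders. This is inferred from Sections 6.1, 6.4 and 10.2. The investigator knows the totals and all past allocations, and guesses the arm with more places left.

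**Correct guesses, all 20 used.** m + 2^(2m−1)/C(2m,m) − 1/2 = 10 + 524,288/184,756 − 0.5 = 10 + 2.84 − 0.5 = 12.34, against 10 by chance. By position (hypergeometric probability of each count, times the larger number of places left over the total left):

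| Patient | Guess correct |
|---|---|
| 1 | 50% |
| 10–11 | 58.6% |
| 16–17 | 66.7% |
| 18–19 | 73.7% |
| 20 | 100% |

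**Certain assignments.** The expected number is 2m/(m+1) = 20/11 = 1.82. P(last k all fixed) = 2·C(20−k,10)/C(20,10): 47.4% for k = 2, 21.1% for k = 3, 8.7% for k = 4.

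**Early stop (Section 10.2).** Dropping the last positions from that sum leaves 0.82 certain assignments at 19 patients, 0.34 at 18 and 0.05 at 16. At 16 patients, 57.5% of guesses are still correct.

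**Change of custody only.** The count is unaffected: still 12.34 and 1.82.

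**Illustrative bias.** Assume that patients enrolled when IB is behind would gain η more than average, those enrolled when GB is behind η less, and those enrolled at a tie the average. The documents give no value for η; 0.10 m/s is an assumption, and the bias scales in proportion to it. For the 10+10 list the bias is (correct − wrong)/10 × η = (12.34 − 7.66)/10 × η = 0.468η. The other two rows are from 200,000 simulated lists each.

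| Allocation of 20 patients | Correct guesses | Certain | Bias / η | Bias at η = 0.10 m/s |
|---|---|---|---|---|
| 10+10 shuffle | 12.34 | 1.82 | 0.468 | 0.047 m/s |
| First 20 of a 20+20 shuffle | 10.7 | 0 | 0.281 | 0.028 m/s |
| Coin toss | 10.0 | 0 | 0.234 | 0.023 m/s |

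The coin toss cannot be predicted, yet the same rule biases it, because patients are selected on the running count. The part due to fixed totals is (0.468 − 0.234) × 0.10 = 0.023 m/s. With the longer list it is (0.281 − 0.234) × 0.10 = 0.005 m/s.

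**Price of the longer list.** With the first 20 of 20+20 the split is hypergeometric(40, 20, 20). P(7:13 or worse) = 11.3% and P(6:14 or worse) = 2.6%. The variance of the arm difference rises by a factor of 1.028 on average; at 7:13 it is (1/7 + 1/13)/0.2 = 1.10.

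**Small blocks.** Known blocks of four would give (20/4) × (2 + 8/6 − 0.5) = 14.17 correct guesses and (20/4) × 4/3 = 6.67 certain assignments, which is worse.

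**The case against.** - **Counting is secondary.** While the investigator holds the list, nothing needs to be counted. That is right. Custody comes first, and the countdown is what remains after it.
- **The list composition is inferred.** Section 6.4 does not give the entries. If replacements under Section 7.4 take the next envelope, a list of 20 runs out or the 10:10 end shifts; if they inherit the drop-out's arm, that assignment is known before consent. This stands as a condition on the numbers, and is itself a reason to specify both points.
- **Room for steering is limited.** New arrivals are approached on day 2, doctors re-check eligibility, and the fixed end date makes deferring patients costly. This stands; the freedom lies mainly with current inpatients.
- **The pilot is descriptive.** Exact balance may reasonably be preferred at 20 patients, and Section 10.1 already limits what will be concluded. This lowers the weight, but the effect size is still meant for planning the next trial.

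A reader might infer that late assignments are generally known. They are not: patients 16–19 are guessed correctly 67–74% of the time, and certainty is confined to the last one or two. A reader might also set 0.047 m/s against the 0.18 m/s in Section 5.1. That figure is a threshold for improvement in walking speed and not a between-arm target, so the ratio has no meaning; about half of the 0.047 m/s would arise under a coin toss anyway. Nor would such selection necessarily be invisible. The screening log (12.1.1) and the baseline tests, set against consent order and running count, could give a hint of it. With ten per arm they could hardly separate it from chance.

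**Conclusion.** The concern holds in limited form. The statement in Section 7.3 that allocation cannot be manipulated is not supported by the procedure described there: upcoming assignments can be known from the list and, with fixed totals, anticipated from the count even without it. For an assumed 10+10 shuffle with all 20 envelopes used, the countdown is worth 2.3 extra correct guesses in 20 and 1.8 certain assignments. Certainty almost disappears if recruitment stops at 16. The bias that fixed totals add is about 0.023 m/s, and it rests on an assumed 0.10 m/s and on consistent steering. Nothing in the documents suggests that the investigator has steered or intends to; the point is that the design does not exclude it. The change should be made because it is cheap, with list custody ahead of list length.

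**What to change.** - **Sections 6.4 and 7.3:** have a person not involved in enrolment generate, seal and hold a new list, and remove the investigator's access to it. Delete or correct the sentence on manipulation.
- **Same sections:** generate the list from more labels than will be used (for example 20 IB and 20 GB), do not disclose its length or composition to the investigator, use envelopes strictly in order and stop at 20 patients. Do not use small blocks.
- **Section 6.1, Section 10.2 and the synopsis:** replace exactly ten per arm with about ten per arm, 20 in total.
- **Section 7.4:** state that a replacement takes the next unopened envelope and does not inherit the drop-out's arm.

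The cost is one new list, 20 more envelopes, an uninvolved person to prepare and keep them, and wording changes; no extra patients. Exact balance is given up: an 11% chance of 7:13 or worse, 2.6% of 6:14 or worse, and about 3% more variance on average. The change may need ethics committee approval under Section 2.8. It reduces the bias from steering but does not remove it.

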## 7.5 General

### Standard therapy

According to the payer, the therapy is individually composed of the following therapies:

Individual Therapies: Speech Therapy (45min), Physiotherapy (30-45), Occupational Therapy (30-45), Neuropsychology (30-180), Physical Therapy (30-60)

Group therapies: Seating group (30), MTT (60), endurance group (45), self-training (30), water aerobics (30), fine motor skills (45), memory group (45), public transport group (135), cooking group (150), arm-hand Group (45), Household Group (45)

Of these, 3-4 therapies are selected Monday-Friday.

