## 8 TEST METHODS

### 8.1 Schedule of study, Table of study measures

one day before arrival	

• Screening of the remittance findings

Day of arrival	

• Admission by the doctors, nursing and physiotherapy --> Screening Inclusion / Exclusion

2nd Day	

• Discussion and presentation of the consent form

• Information to the therapist that the patient may be eligible

• in physiotherapy only BBS and 10 m walk test if patient has already signed

from the 2nd day	

• Signing of consent (SC)

Day of SC	

• Envelopes draw IB or GB for the allocation

• Report to the scheduling about allocation and notification of the patient

SC +1d	

• Assessment Primary target: Gait speed through 10 m walk test

• Assessment secondary target: Fall risk due to BBS, walkability due to FAC

SC +2d	

• IB or GB so that it can be found twice a week (see point 8.2)

6. IB/GB	

• next day reassessments

• 10 m walk test, BBS, FAC

Visitation	

• see point visitation plan

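### Staff who know the allocation can plan or change the ordinary therapy programme, and the plan neither names the other therapy received as data nor compares it between arms

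*Combined protocol and SAP*

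**What the plan says.** All places are in the combined protocol and SAP.

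- **Order of events.** Section 6.1 runs from consent to allocation to planning: "With the signed consent, the randomization and accordingly the planning of the therapies, including initial and reassessment". The table in section 8.1 has the envelope drawn on the day of consent, followed by "Report to the scheduling about allocation and notification of the patient".
- **Who knows the arm.** Section 6.1 adds: "With the allocation, the therapists will also be informed, since they are not allowed to do any additional balance training in the therapy". Section 6.5 states: "There is no blinding. Compliance with the blinding is hardly feasible in this setting".
- **Ordinary programme.** Section 7.5 (Standard therapy) says: "According to the payer, the therapy is individually composed of the following therapies", and after the menu: "Of these, 3-4 therapies are selected Monday-Friday". The menu includes physiotherapy (30-45 min), physical therapy (30-60), MTT (60), endurance group (45) and water aerobics (30). It also includes speech therapy, neuropsychology, and memory and cooking groups.
- **Limits on other therapy.** The synopsis says for both arms: "In physiotherapy and occupational therapy no balance training may be performed during the intervention period". Sections 3.4, 7.6.1, 7.6.2 and 7.9 also deal only with balance training. Section 7.9 drops the seat-and-stand group in both arms.
- **Data and analysis.** The visitation plan has rows for the test intervention and for medication, but none for other therapies. The source-data list in section 12.1.2 names details of the intervention and concomitant medication, but not concomitant therapy. Section 10 describes the assessments, an odds ratio, a sample-size calculation and a discussion of bias. It mentions no comparison of therapy received.

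**The concern.** The exercise sequence is the same in both arms (section 7.5.2), so the setting, individual or group, is the only intended contrast. The primary outcome is walking speed, measured over about three weeks of inpatient rehabilitation in which most therapy time lies outside the trial sessions.

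The plan leaves walking, strength and endurance work free to vary, and people who know the arm can choose or adjust it. If that work differed between arms, the difference would enter the comparison of walking speed and look like an effect of setting. It could push the result either way: extra walking practice for group patients would hide a benefit of individual training, and extra practice for individual patients would create one.

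Two stated aims are exposed. Section 10 takes the sample size of the follow-up trial from these data, and section 10.3 makes bias the main subject of the analysis. Section 6.3, on minimising bias, does not mention the other therapies, and the compliance check in section 7.7 asks only about extra balance exercises.

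**Working it through.** **Inputs from the documents**

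- Study sessions: "The patients receive 2x weekly individual balance training for 25 minutes each" (synopsis; the group arm has the same frequency and length), for three weeks (section 6.1).
- Other therapies: 3-4 per weekday (section 7.5). The synopsis says at least 3 and gives no upper limit.
- Patients: 10 per arm (section 10.2).

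**Assumptions**

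- Three weeks are 15 weekdays.
- A typical other session lasts 30-45 minutes. Several menu items are longer.
- Physiotherapy, physical therapy, MTT, endurance and water groups count as walking-related. The documents do not label them so.

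**1. Trial dose.** 2 per week x 3 weeks = 6 sessions, which matches the six units in sections 7.6.1 and 7.6.2. 6 x 25 = 150 minutes.

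**2. Other therapy in the same period.**

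- Lower end: 3 x 15 = 45 sessions; 45 x 30 = 1,350 minutes.
- Upper end: 4 x 15 = 60 sessions; 60 x 45 = 2,700 minutes.

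**3. Trial dose relative to the background.** 150 / 1,350 = 11.1% and 150 / 2,700 = 5.6%, so about 6-11%.

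**4. What small changes amount to.**

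- One extra 60-minute session a week: 3 x 60 = 180 minutes.
- One extra 30-45 minute session a week: 3 x 30 = 90 to 3 x 45 = 135 minutes.

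A modest change by informed staff is thus of the same order as the trial dose. It may fall below or above it.

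**5. Chance alone.** With a between-patient SD of walking-related minutes, the standard error of the arm difference is SD x sqrt(2/10). The documents give no SD, so the range below is assumed.

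| Assumed SD (min) | SE (min) | Probability that arm means differ by more than 150 min |
|---|---|---|
| 100 | 44.7 | 0.1% |
| 150 | 67.1 | 2.5% |
| 200 | 89.4 | 9% |
| 300 | 134.2 | 26% |

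This part is random variation. Planning after the draw does not cause it, and moving the planning would not remove it. Recording the minutes would show it.

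**6. Is the information captured?** Setting the visitation plan, section 12.1.2 and section 10 side by side, no named item holds the type or minutes of other therapy, and no analysis uses them.

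**The case against.** **The sentence in section 6.1 is ambiguous.** It may mean only the trial slots and assessments, since those are the items it names. The synopsis time plan supports this: after the draw, the patient is scheduled for balance training twice a week. The ordinary programme is described as prescribed and depends on the payer, physiotherapy is already running on day 2 (section 8.1), and existing inpatients may be recruited (section 7). A reader might infer that all 3-4 daily therapies are planned only after the envelope is opened. The documents do not support that. What stands is that the programme can be planned or changed by informed staff, because nothing confines the planning to trial slots or fixes the rest.

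**The size is easily overstated.** A reader might infer that planning after the draw can make the arms differ by more than the whole trial dose, or set 3 against 4 therapies a day and obtain a multiple of it. That comparison counts every therapy on the menu, including speech and cooking. Chance imbalance is not a result of the planning, and one compensating 30-45 minute session a week comes to only 90-135 minutes.

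**Some records may exist.** A reader might infer that no study data would show a difference. That is too absolute: the intervention details in section 12.1.2, the general CRF scope in section 12.1.1 and the clinic's schedules could hold the information. The accurate statement is that it is not named and not analysed.

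**The trial is open.** Therapists may have to know the arm, since section 7.9 words the balance ban separately for each arm, and colleagues can enter the group room (section 6.5). This limits what masking could achieve. It is no argument against recording.

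**It is a descriptive pilot of 20 patients.** True, but section 10.3 makes bias its main analysis.

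**Conclusion.** The concern holds in this limited form. Staff who know the allocation can plan or change the ordinary programme, only balance training is restricted, and the plan neither names the type and minutes of other therapy as data nor compares them by arm. A difference in them could be mistaken for an effect of setting.

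The trial dose of 150 minutes is about 6-11% of the surrounding therapy, so one extra hour a week (180 minutes) would exceed it. This rests on 15 weekdays, sessions of 30-45 minutes and the assumption that the named therapies affect walking speed. The documents contain no evidence that a difference will arise, nor its direction or likely size. The case for change rests on the low cost of guarding the only intended contrast.

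**What to change.** **(a) Record the plan before the draw.** In sections 6.1 and 8.1, state that the ordinary therapy plan (types and weekly minutes) is written down before the envelope is opened. After the draw, scheduling adds only the two weekly IB or GB slots and the reassessment (and the initial assessment where, as in section 8.1, it still follows the draw). Later changes for clinical need remain open and are dated. For existing inpatients, record the plan already running.

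**(b) Record and report what was delivered.** Copy the delivered type and minutes of each patient's other therapies from the existing schedules into the data table. Report them by arm in the section 10.3 bias analysis, and name the item in section 12.1.2.

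**Optional, with limited gain.** Give the treating therapists one neutral instruction for both arms: the patient is in the trial, and no balance training takes place outside trial sessions. Section 7.9 would then have to be reconciled, because it words the ban by arm.

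**Cost.** One step moved ahead of the draw and a little extra data entry for 20 patients. No therapy is withheld. Staff may still learn the arm from patients or the open group room, so (a) reduces the opportunity for informed planning but does not remove it, and (b) is needed to show what happened.
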